#### **16.1.1.2 Severity**

Document:

\\\ieedc-vnasc01\Biosdata\Reistone\SHR0302\CZA55021\Biostatistics

Author:

[REDACTED]

Version Number:

Final v1.2

Version Date:

23Mar2021

Template No: CS\_TP\_BS016 Revision 5  
Effective Date: 01Apr2018

Reference: CS\_WI\_BS005

The severity of TEAE will be collected as mild, moderate and severe. All TEAEs in treatment phase will be summarized by SOC, PT, and severity for each SHR-0302 dose level and placebo. If a patient reports a TEAE more than once within that SOC/ PT, the AE with the worst case severity will be used in the corresponding severity summaries. All TEAEs will also be summarized similarly for 8 mg QD total, 4 mg BD total, 4 mg QD total, placebo only and overall during the whole study period.

### **16.1.2 TEAEs of Serious Infection**

A serious infection during the study is defined as any infection (viral, bacterial, and fungal) requiring hospitalization or parenteral antimicrobials. The patient must be discontinued from the study. Serious infection will be identified as those records with a response of "Yes" to the item "Is this a serious infection defined in protocol?" on the "Adverse Events" form of the eCRF. Serious Infection in treatment phase will be summarized by SOC and PT for each SHR0302 dose level , placebo and overall. The number of patients with at least one serious infection will be presented and 95% CI will be calculated using the Clopper-Pearson method. TEAEs of serious infection will also be summarized similarly for 8 mg QD total, 4 mg BD total, 4 mg QD total, Placebo only and overall during the whole study period.

### **16.1.3 TEAEs Leading to Study Discontinuation**

TEAEs leading to study discontinuation will be identified as those records with a response of "Yes" to the item "Did the adverse event cause the patient to be discontinued from the study?" on the "Adverse Events" form of the eCRF. Summaries of patients (frequencies and percentages) with TEAEs leading to study discontinuation and summaries of incidence rates (frequencies) in treatment phase by SOC and PT will be prepared for each SHR0302 dose level, placebo and overall. TEAEs leading to study discontinuation will also be summarized similarly for 8 mg QD total, 4 mg BD total, 4 mg QD total, Placebo only and overall during the whole study period.

A listing will be prepared for TEAEs leading to study discontinuation.

### **16.1.4 Serious Adverse Events (SAEs)**

A serious adverse event is any untoward medical occurrence that, at any dose:

- a. Results in death
- b. Is life-threatening
- c. Requires hospitalization or prolongation of existing hospitalization
- d. Results in disability/incapacity, or
- e. Is a congenital anomaly/birth defect

Document: \\ieedc-vnasc01\Biosdata\Reistone\SHR0302\CZA55021\Biostatistics

Author: [REDACTED]

Version Number:

Final v1.2

Version Date:

23Mar2021

Template No: CS\_TP\_BS016 Revision 5

Effective Date: 01Apr2018

Reference: CS\_WI\_BS005

- f. Medical or scientific judgement should be exercised in deciding whether reporting is appropriate in other situations, such as important medical events that may not be immediately life-threatening or result in death or hospitalization but may jeopardize the patient or may require medical or surgical intervention to prevent one of the other outcomes listed in the above definition. These should also be considered serious. Examples of such events are invasive or malignant cancers, intensive treatment in an emergency room or at home for allergic bronchospasm, blood dyscrasias or convulsions that do not result in hospitalization, or development of drug dependency or drug abuse.
- g. All events of possible drug-induced liver injury with hyperbilirubinaemia defined as ALT  $\geq$  3xULN and bilirubin  $\geq$  2xULN ( $>35\%$  direct) (or ALT  $\geq$  3xULN and INR  $>1.5$ , if INR measured) termed 'Hy's Law' events (INR measurement is not required and the threshold value stated will not apply to patients receiving anticoagulants).

On the Adverse Events page of the eCRF, serious adverse events are those events respond as "Yes" for item "Serious Criteria".

Summaries of all serious TEAEs and serious TEAEs Related to study medication in treatment phase by SOC and PT for each SHR0302 dose level, placebo and overall will be prepared. All serious TEAEs and serious TEAEs related to study medication will also be summarized similarly for 8 mg QD total, 4 mg BD total, 4 mg QD total, Placebo only and overall during the whole study period. Patients with missing relationship will be treated as probably related.

Listings will include all SAEs (serious TEAEs and serious Non-TEAEs). Listings for SAEs will include the start date, end date, severity, severity, relationship to study drug, action taken, outcome, SAE criteria, and a liver event or not, etc.

### 16.1.5 TEAEs Leading to Death

TEAEs leading to Death are those TEAEs which are recorded as "Fatal" on the Adverse Events page of the eCRF. A summary of TEAEs leading to death in treatment phase by SOC and PT will be prepared for each SHR0302 dose level, placebo and overall. TEAEs leading to death will also be summarized similarly for 8 mg QD total, 4 mg BD total, 4 mg QD total, Placebo only and overall during the whole study period. A listing will be prepared for TEAEs leading to death.

## 16.2 DEATHS

If patients die during the study as recorded on the "Death Details" page of the eCRF, the information will be presented in a summary table for each SHR0302 dose level, placebo

Document: \\ieedc-vnasc01\Biosdata\Reistone\SHR0302\CZA55021\Biostatistics

Author: [REDACTED]

Version Number:

Final v1.2

Version Date:

23Mar2021

Template No: CS\_TP\_BS016 Revision 5  
Effective Date: 01Apr2018

Reference: CS\_WI\_BS005

and overall. Death information will also be summarized similarly for 8 mg QD total, 4 mg BD total, 4 mg QD total, Placebo only and overall during the whole study period. Death information will be presented in a data listing for SS.

### 16.3 LABORATORY EVALUATIONS

Results from the central laboratory will be included in the reporting of this study for Hematology, Chemistry, Urinalysis and Others. All laboratory assessments will be listed in the outputs.

Presentations will use SI Units. All laboratory data will be summarized and listed for all patients in the SS set by visits where data are collected.

Quantitative laboratory measurements reported as “< X”, i.e. below the lower limit of quantification (BLQ), or “> X”, i.e. above the upper limit of quantification (ULQ), will be converted to X for the purpose of quantitative summaries, but will be presented as recorded, i.e. as “< X” or “> X” in the listings.

Quantitative laboratory measurements will be compared with the relevant laboratory reference ranges in SI units and categorized as:

- Low: Below the lower limit of the laboratory reference range.
- Normal: Within the laboratory reference range (upper and lower limit included).
- High: Above the upper limit of the laboratory reference range.

The following summaries will be provided for laboratory data:

- Actual and change from baseline by visit (for quantitative measurements)
- Incidence of abnormal values according to normal range criteria
- Shift tables representing categorical change of laboratory evaluation results from baseline to each post baseline
- Listing of patients with laboratory results

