5.9 Stopping Criteria

The stopping safety criteria are as below: Subject who fulfil the following criteria should discontinue the study.

- Liver chemistry threshold stopping criteria have been designed to assure subject safety and to evaluate liver event etiology (in alignment with the FDA premarketing clinical liver safety guidance) Study treatment will be stopped if the liver chemistry stopping criteria is met. Refer to [Section 7.3.9 Liver Chemistry Stopping and Follow-up Criteria](#).
- A subject that meets the QTc criteria below will be withdrawn from the study. The QT correction formula used to determine discontinuation should be the same one used throughout the study.

-QTc, QTcB/QTcF > 500 ms

-Change from baseline: QTc >60 ms

Use the averaged QTc values of the 3 ECGs to determine whether the subject should be discontinued from the study.

- Abnormal laboratory values of interests. (modified from CTCAE 5.1 criteria)
 - Hemoglobin (Hgb) <7.0 g/dL; or when blood transfusion is indicated.
 - Neutrophil count < 500/mm³
 - Platelet count < 25,000/mm³
 - Lymphocyte count < 200/mm³
 - Leukocyte count < 2000/mm³
- Subject who develops Venous Thrombosis (eg Deep Vein Thrombosis).
- Subject who develops Pulmonary Embolism.
- Subject who develops Cerebrovascular Events (eg Thromboembolic Stroke, Transient Ischemic Attack (TIA), Myocardial Infarction)
- An unacceptable adverse event, as determined by the Investigator and the medical monitor.
- Any unacceptable adverse event that is thought to be related to the investigational product may result in the study being terminated.
- Significant protocol deviation. The discovery that post-randomization the subject failed to meet protocol entry criteria or did not adhere to protocol requirements, and continued participation poses an unacceptable risk to the subject's health.
- If the subject is found to be pregnant, the subject must be withdrawn immediately. The procedure is described in [Section 7.3.10](#).

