7.3.9 Liver Chemistry – Stopping and Follow-up Criteria

Phase II liver chemistry stopping and follow up criteria have been designed to assure subject safety and evaluate liver event etiology (in alignment with the FDA premarketing clinical liver safety guidance).

Phase II liver chemistry stopping criteria 1-5 are defined below:

1. ALT $\geq 3 \times \text{ULN}$ **and** bilirubin $\geq 2 \times \text{ULN}$ ($>35\%$ direct bilirubin) (or ALT $\geq 3 \times \text{ULN}$ **and** INR >1.5 , if INR measured).

NOTE: if serum bilirubin fractionation is not immediately available, study drug should be discontinued if ALT $\geq 3 \times \text{ULN}$ **and** bilirubin $\geq 2 \times \text{ULN}$. Serum bilirubin fractionation should be performed if testing is available. If testing is unavailable, **record presence of detectable urinary bilirubin on dipstick**, indicating direct bilirubin elevations and suggesting liver injury.

2. ALT $\geq 5 \times \text{ULN}$.

3. ALT \geq 3xULN if associated with the appearance or worsening of symptoms of hepatitis or hypersensitivity such as fatigue, nausea, vomiting, right upper quadrant pain or tenderness, fever, rash or eosinophilia.
4. ALT \geq 3xULN persists for \geq 4 weeks.
5. ALT \geq 3xULN and cannot be monitored weekly for 4 weeks

When any of the liver chemistry stopping criteria 1-5 is met, do the following:

- **Immediately** withdraw investigational product.
- Report the event to Reistone/designated CRO **within 24 hours** of learning its occurrence.
- Complete the liver event eCRF and SAE data collection tool if the event also meets the criteria for an SAE. All events of ALT \geq 3xULN **and** bilirubin \geq 2xULN ($>35\%$ direct bilirubin) (or ALT \geq 3xULN **and** INR >1.5 , if INR measured; INR measurement is not required and the threshold value stated will not apply to patients receiving anticoagulants), termed 'Hy's Law', **must be reported as an SAE (excluding studies of hepatic impairment or cirrhosis)**.

NOTE: if serum bilirubin fractionation is not immediately available, study drug should be discontinued if ALT \geq 3xULN **and** bilirubin \geq 2xULN. Serum bilirubin fractionation should be performed if testing is available. If testing is unavailable, **record presence of detectable urinary bilirubin on dipstick**, indicating direct bilirubin elevations and suggesting liver injury.

- Complete the liver imaging and/or liver biopsy eCRFs if these tests are performed

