- Perform liver event follow up assessments, and monitor the subject until liver chemistries resolve, stabilize, or return to baseline values as described below.
- Withdraw the subject from the **study** (unless further safety follow up is required) after completion of the liver chemistry monitoring as described below.
- Do not re-challenge with investigational product.

In addition, for criterion 1:

- Make every reasonable attempt to have subjects return to clinic within **24 hours** for repeat liver chemistries, liver event follow-up assessments (see below), and close monitoring.
- A specialist or hepatology consultation is recommended.

- Monitor subjects twice weekly until liver chemistries (ALT, AST, alkaline phosphatase, bilirubin) resolve, stabilise or return to within baseline values

For criteria 2, 3, 4 and 5:

- Make every reasonable attempt to have subjects return to clinic **within 24-72 hrs** for repeat liver chemistries and liver event follow up assessments (see below)
- Monitor subjects weekly until liver chemistries (ALT, AST, alkaline phosphatase, bilirubin) resolve, stabilize or return to within baseline values; criterion 5 subjects should be monitored as frequently as possible.

Subjects with $\text{ALT} \geq 3 \times \text{ULN}$ **but** $< 5 \times \text{ULN}$ **and** bilirubin $< 2 \times \text{ULN}$, without hepatitis symptoms or rash, and who can be monitored weekly for 4 weeks:

- Notify the Reistone/designated CRO medical monitor within 24 hours of learning of the abnormality to discuss subject safety.
- Can continue investigational product.
- Must return weekly for repeat liver chemistries (ALT, AST, alkaline phosphatase, bilirubin) until they resolve, stabilise or return to within baseline.
- If at any time these subjects meet the liver chemistry stopping criteria, proceed as described above.
- If, after 4 weeks of monitoring, $\text{ALT} < 3 \times \text{ULN}$ and bilirubin $< 2 \times \text{ULN}$, monitor subjects twice monthly until liver chemistries normalize or return to within baseline values.

For criteria 1-5, make every attempt to carry out the **liver event follow up assessments** described below:

- Viral hepatitis serology including:
 - Hepatitis A IgM antibody;
 - Hepatitis B surface antigen and Hepatitis B Core Antibody (IgM);
 - Hepatitis C RNA;
 - Cytomegalovirus IgM antibody;
 - Epstein-Barr viral capsid antigen IgM antibody (or if unavailable, obtain heterophile antibody or monospot testing);

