## 6.4 UNSCHEDULED VISITS, RETESTS AND EARLY TERMINATION DATA

In general, for by-visit summaries, data recorded at the nominal visit will be presented. Unscheduled measurements will not be included in by-visit summaries but will contribute best/ worst case value where required .

In the case of a retest (same visit number assigned), the latest available measurement for that visit will be used for by-visit summaries.

Listings will include scheduled, unscheduled, retest and early discontinuation data.

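### No laboratory table named in the SAP text counts, by arm, the patients who reach the protocol's haematology or liver limits; one worst-value table would fill the gap.

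*SAP*

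**What the plan says.** SAP 16.3 sorts each quantitative laboratory value into Low, Normal or High against the reference range. It names four outputs: actual values and changes by visit, "Incidence of abnormal values according to normal range criteria", shift tables from baseline to each post-baseline point, and a listing. Its general rule is "All laboratory data will be summarized and listed for all patients in the SS set by visits where data are collected".

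SAP 6.4 adds two rules. The first is "Unscheduled measurements will not be included in by-visit summaries", though such values may feed a best or worst case where one is required; 16.3 requires none. The second is that, for a retest under the same visit number, "the latest available measurement for that visit will be used for by-visit summaries".

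The protocol sets numerical limits of its own. Section 5.9 lists haematology values at which a subject should discontinue, the first being "Hemoglobin (Hgb) <7.0 g/dL; or when blood transfusion is indicated", followed by limits for neutrophils, platelets, lymphocytes and leukocytes. Section 7.3.9 states "Phase II liver chemistry stopping criteria 1-5 are defined below"; these include ALT at or above 5 times ULN, and ALT at or above 3 times ULN with bilirubin at or above 2 times ULN. A patient with ALT from 3 to below 5 times ULN, bilirubin below 2 times ULN and no hepatitis symptoms or rash "Can continue investigational product" if weekly monitoring is possible, and "Must return weekly for repeat liver chemistries".

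Elsewhere the SAP does tabulate against clinical limits: 16.4.1 counts maximum QTcF by arm, including above 500 msec and a rise above 60 msec, and 16.5.1 sets markedly abnormal criteria for vital signs. For liver events, 16.7 refers to protocol 7.3.9 but provides listings only.

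**The concern.** The reference range and the protocol limits answer different questions. Low/Normal/High shows who is outside normal, not how far. Two kinds of patient are hidden: one already abnormal at entry who crosses a limit without a category shift, and one normal at entry who lands in the same cell whether the change is trivial or severe. A peak between visits, or one overwritten by a same-visit retest, is absent from the by-visit tables.

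SAP 3.1 presents JAK1 selectivity as a benefit-risk advantage and says the trial's data will serve to choose one or two doses. Protocol 1.1 links JAK2 inhibition to anaemia and thrombocytopenia. The number of patients per arm who reach a protocol limit describes that risk directly, and under the SAP text a reader would have to rebuild it from listings.

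**Working it through.** The documents state no figure to reproduce, because the point concerns which tables are specified. The checks are as follows.

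1. **Can a limit be crossed without a category shift?** Protocol 5.3 (criteria 9 and 10) admits haemoglobin from 9.0 g/dL and ALT up to 2 times ULN.
   - ALT: from 2 times ULN, 3/2 = a 1.5-fold rise reaches 3 times ULN and 5/2 = a 2.5-fold rise reaches 5 times ULN. Both are High to High, as is 1.5 to 6 times ULN.
   - Haemoglobin: 9.0 − 7.0 = 2.0 g/dL, so a fall of just over 2.0 crosses the limit. A fall from 9.5 to 6.9 is Low to Low, assuming the laboratory's lower limit of normal is above 9.5 (the documents give no range).
   - From a normal baseline, ALT of 1.1 or 6 times ULN is Normal to High either way.

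2. **How many required rechecks fall between visits?** Treatment-phase laboratory visits are at days 7, 28 and 56 (protocol 5.12).
   - Raised ALT at week 1: weekly rechecks on days 14, 21, 28, 35; only day 28 is scheduled.
   - Raised ALT at week 4: days 35, 42, 49, 56; only day 56 is scheduled.
   - In each case 3 of 4 are unscheduled. The first crossing of 3 times ULN is at a scheduled visit in both examples, so it enters the by-visit data unless a same-visit retest replaces it. What the by-visit tables lose is any further rise between visits, or a first crossing found at an unscheduled test.

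3. **What would the specified summaries show of a few crossings?** This is an illustration with 152/4 = 38 patients per arm, k of whom lose 3.1 g/dL of haemoglobin while the rest are unchanged.
   - Shift in arm mean = k × 3.1/38: 0.082 (k = 1), 0.163 (k = 2), 0.245 g/dL (k = 3). The median does not move.
   - Standard error of a between-arm difference = SD × √(2/38): 0.184 for SD 0.8 and 0.275 for SD 1.2. The SD of change is assumed; the documents give none.
   - The minimum is the same whether one or three patients fall that far.
   - A direct count reads 3/38 = 7.9%, exact (Clopper-Pearson) 90% CI 2.2% to 19.2%.

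4. **How much can counts of this size tell?** At assumed true rates of 2% and 5%, the chance of at least one case in 38 is 1 − 0.98^38 = 54% and 1 − 0.95^38 = 86%. An observed 0/38 still allows up to 1 − 0.05^(1/38) = 7.6% (one-sided 95%).

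**The case against.** The strongest reply is that little is hidden. Protocol 7.3.12 counts an abnormal laboratory finding as a possible adverse event, and SAP 16.1.1 and 16.1.1.2 tabulate all treatment-emergent events by arm, by SOC/PT and by severity. Hy's Law events are mandatory SAEs, and events leading to discontinuation are also tabulated by arm. By-visit minima and maxima of actual values would show an extreme at a scheduled visit, every laboratory result is listed, and an independent safety committee meets at least twice. All this stands. None of it counts a laboratory limit, however, and the adverse event route depends on what each investigator reports. A patient with ALT from 3 to below 5 times ULN who stays on drug need not reach the SAE or discontinuation tables.

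A reader might infer that the SAP breaches the protocol. It does not: protocol 9.3.4.4 asks for observed values, changes, flagged abnormalities and shift tables, and SAP 16.3 covers these. The limits in 5.9 and 7.3.9 are rules for managing patients, not declared endpoints.

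A reader might also infer from the 3-of-4 figure that most liver peaks are lost. The documents do not support that either. Both examples begin at a scheduled visit, the retest rule applies only to repeats given the same visit number, and nothing shows that weekly rechecks are coded so. The incidence line in 16.3 does not itself say it is by visit; if it pooled all post-baseline values, unscheduled peaks could enter it, but still judged only against the normal range.

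The dose-selection argument is also uneven. The JAK2 concern is haematological, and the 5.9 haematology limits came with Amendment 03 while the SAP is based on protocol v3.0, so that half may be a missed update. The liver half has no such explanation: SAP 16.7 itself cites 7.3.9.

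**Conclusion.** The point holds as a gap in descriptive safety reporting. No table named in the SAP text gives, by arm, the number of patients reaching the protocol's haematology or liver limits, and the Low/Normal/High tables cannot supply it. Whether such a table exists in the output templates (SAP 8) cannot be settled, because they are not in the documents. It would go too far to say that safety signals will be missed: the data are collected and listed, and several indirect by-arm summaries remain.

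The size is modest. Arms of about 38 give small counts that separate doses poorly, and the event rates, the SD of change and the three-patient example are assumptions. The primary analysis is unaffected. This is a cheap improvement.

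**What to change.** Check the output templates first. If the table is not there, keep the 16.3 outputs and add one descriptive count-and-percentage table by arm, for the treatment phase and for the whole-study total groups defined in SAP 16.1.1. It should count patients whose worst post-baseline value, including unscheduled values and every retest, reaches each of these limits:

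- haemoglobin <7.0 g/dL;
- neutrophils <500, platelets <25,000, lymphocytes <200 and leukocytes <2000 per mm³;
- ALT ≥3×ULN; ALT ≥5×ULN; ALT ≥3×ULN with bilirubin ≥2×ULN.

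Show the baseline category (Low/Normal/High) alongside. Protocol Table 3 lists lymphocytes only as a percentage, so the SAP should define the absolute count as WBC × percentage/100.

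The cost is a paragraph of SAP text and a little programming on values already collected. The downside is small counts, to be labelled as descriptive only.

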### 16.4 ELECTROCARDIOGRAM (ECG) EVALUATIONS

12-lead ECGs will be recorded in triplicate at the scheduled time points. The three values of each ECG parameter at each visit will be averaged to determine time-specific parameter for a patient and used in summaries. The three values of each ECG parameter at each visit will be

included in listings.

The following ECG parameters will be reported for this study:

- Heart Rate (Beats/min)
- PR Interval (msec)
- RR Interval (msec)
- QRS interval (msec)
- QT Interval (msec)
- QTc(F) Interval (msec)
- Overall assessment of ECG
  - Normal
  - Abnormal Not Clinically Significant (ANCS)
  - Abnormal Clinically Significant (ACS)

The following summaries will be provided for ECG data:

- Actual and change from baseline by visit (for quantitative measurements)
- Incidence of abnormal and clinically significant values
- A shift analysis table showing shift in overall ECG interpretation from baseline to each time point

